1.0 Objectives*

- 1.1 The purpose of this investigation is to determine the effect, if any, core activation and stabilization training may have on the gait and function of patients diagnosed with knee osteoarthritis (KOA).

The specific aims of this investigation include:

Specific Aim 1: Determine if kinetic (time to first peak ground reaction force [T_1] and second peak ground reaction force [F_2], both in the sagittal plane, and external knee adduction moment [KAM]) and kinematic (peak stance knee flexion angle [KFA]) gait variables, and speed, differ between patients with KOA and age and gender matched controls during self-selected paced ambulation, and determine which ones have predictive relationships with Knee Injury and Osteoarthritis Outcome Score (KOOS) scores in the patients with KOA.

Specific Aim 2: Determine if volitional core activation alters gait kinetics (T_1 , F_2 , and KAM), kinematics (KFA), and speed in patients with and without KOA during self-selected paced ambulation when compared to ambulating without volitional core activation, and whether the subjective pain complaints are significantly changed in the group with KOA. Determine whether there are baseline differences in core activation between those with and without KOA.

Specific Aim 3: Determine if a six-week core stabilization program alters KOOS score, and the kinetics (T_1 , F_2 , and KAM), kinematics (KFA), and speed of gait in patients with KOA during self-selected paced ambulation as compared to their pre-intervention baselines. Determine if there is a predictive relationship between the number of completed intervention sessions performed and these observed changes.

- 1.2 The alternate hypotheses for each specific aim include the following:

Specific Aim 1:

H_1 : Participants with KOA will have significant differences in lower extremity kinetics (T_1 , F_2 , and KAM) and kinematics (KFA), and gait speed, as compared to healthy controls during self-selected paced ambulation.

H_2 : The significant kinetic (T_1 , F_2 , and KAM), kinematic (KFA), and gait speed differences observed in participants with KOA will have a significant predictive relationship to their scores on the KOOS.

PROTOCOL TITLE: The Effects of Core Activation and Stabilization Training on Gait Kinetics, Kinematics, and Speed, and Self-Perceived Function in Patients with Knee Osteoarthritis

Specific Aim 2:

H₁: Gait speed, kinetics (T₁, F₂, and KAM) and kinematics (KFA) will significantly differ with volitional activation of the core during self-selected paced ambulation within the KOA group and between the KOA and control groups.

H₂: Pain, as assessed via a Numeric Pain Rating Scale (NPRS), will significantly differ from baseline with volitional activation of the core during self-selected paced ambulation for patients with KOA.

H₃: There will be a significant difference in the baseline transversus abdominis (TA) activation observed via electromyography (EMG) analysis between and within the control and KOA groups, without and with volitional activation during ambulation.

Specific Aim 3:

H₁: Gait speed, kinetics (T₁, F₂, and KAM), and kinematics (KFA) will significantly differ in participants with KOA during self-selected paced ambulation after a six-week core stabilization program when compared to their baseline.

H₂: Functional ability, as assessed via the KOOS, will significantly differ in participants with KOA from baseline after a six-week core stabilization program.

H₃: The total number of supervised and home exercise sessions in a six-week intervention program will significantly predict changes in gait speed, kinetics (T₁, F₂, and KAM), and kinematics (KFA) in participants with KOA during self-selected paced ambulation.

2.0 Background*

- 2.1 This will be the second investigation by the PI and sub-investigator on this topic, following the promising results of a pilot study on a small sample size (N=5) completed last year. Whether or not core stabilization influences gait impairments in patients with KOA remains to be seen. Core stabilization has been shown to have positive effects, including increased stride velocity and scores on functional tests like the Functional Reach Test and Timed Up and Go, in older adults.¹ Older adults were also shown to have high compliance with a core stability training program.¹ A systematic

PROTOCOL TITLE: The Effects of Core Activation and Stabilization Training on Gait Kinetics, Kinematics, and Speed, and Self-Perceived Function in Patients with Knee Osteoarthritis

review indicated that core training is important to consider when treating older individuals to improve functional use of the extremities, improving participation in activities of daily living, and as part of a fall prevention program.² Additionally, it has been shown to benefit young, active individuals in preventing anterior cruciate ligament injury³ and greater duration of improved outcomes in patients with patellofemoral pain syndrome.⁴ Athletes with decreased core control have been shown to be at an increased risk of knee injury as well.⁵ One potential cause for this is the ability of the core to improve lower extremity kinematics when activated during challenging single leg weight bearing activity.⁶ A recent publication by Azuma, et al. did indicate that paraspinal and anterior abdominal thinning had a negative predictive relationship to the presence of KOA;⁷ however, no investigation has explored a cause and effect relationship between core stability/stabilization training and the presence or severity of KOA, nor the gait and functional ability of patients with KOA. This later concept is the focus of this investigation.

- 2.2 Unpublished pilot data (see 2.1) collected by the same PI and sub-investigator shows that volitional activation of the TA during self-selected paced ambulation significantly decreases the time to first peak ground reaction force (T_1) in the sagittal plane in participants with KOA ([name], [name], unpublished data, May 2018). This same kinetic gait variable is included in this investigation as one of the dependent variables in all three parts of the investigation.
- 2.3 Nearly four percent of the global population has KOA, with the global female percentage nearing five percent. Additionally, the years lived with disability (YLDs) resulting from the disorder increased by 64.8% from 1990 to 2010.⁸ The picture is not much better in the United States, where osteoarthritis ranks eighth highest in YLDs compared to other pathologies.⁹ The rate of KOA has continued to climb here in the U.S., doubling in the past half-century even when accounting for increased life expectancy and higher average BMI,¹⁰ both of which are considered risk factors in the development of KOA.¹¹

Patients with KOA have been shown to have gait abnormalities when compared to healthy controls, including alterations in trunk and pelvic kinematics,¹² lower extremity kinematics^{13,14} and kinetics,¹⁴⁻¹⁸ gait speed,^{13-17,19} and functional outcome measure scores.¹⁹ Some of these differences, like an increased external knee adduction moment (KAM)^{20,21} and a decreased peak stance knee

PROTOCOL TITLE: The Effects of Core Activation and Stabilization Training on Gait Kinetics, Kinematics, and Speed, and Self-Perceived Function in Patients with Knee Osteoarthritis

flexion angle (KFA),¹⁴ have been shown to correlate with the advancement of KOA and may be causative in nature. Others, like an increased T₁¹⁶ and reduced freely chosen gait speed,²² may be compensatory.²³ The same has been found in regard to the reduced second peak ground reaction force in the sagittal plane (F₂) observed in this population.¹⁸

Reduced gait speed alone is predictive of increased fall risk in older adults, without any need to consider additional activities performed during walking tasks.²⁴ Additionally, the gait impairments observed in this population can be so extreme that they can be more limiting than those observed in patients with diagnoses typically considered more severe, like congestive heart failure, diabetes, heart disease, and stroke.²⁵ Therefore, improving function via improving gait speed via novel approaches is indicated, but not at the expense of increasing wear and tear on osteoarthritic joints. This investigation aims to show that core stabilization, which has been shown beneficially influence the kinetics and kinematics of lower extremity movements in younger, more active populations, can serve the same purpose in a population with KOA. The investigators are specifically trying to improve self-perceived function and gait speed, via improving the kinetics and kinematics observed in self-selected ambulation.

3.0 Inclusion and Exclusion Criteria*

- 3.1 Potential participants will be screened for eligibility by the PI once they have expressed interest either by contacting the PI themselves, or upon being referred by someone familiar with the investigation. Assurance of meeting the inclusion and exclusion criteria will be ensured during the informed consent process.
- 3.2 The inclusion and exclusion criteria for this investigation are as follows:

Inclusion criteria:

English-speaking men and women, 40 years old and older, of any race or ethnic group, with a documented diagnosis from a medical provider (i.e., physician, physician assistant, or nurse practitioner, etc.) of KOA, unilaterally or bilaterally. Previous or current physical therapy patients may be included (see exclusion criteria for exceptions). *Healthy controls* will meet the same requirements, but without a medical diagnosis of KOA and have the ability to ambulate on a level surface without any report of pain in their knees at the time of gait assessment.

PROTOCOL TITLE: The Effects of Core Activation and Stabilization Training on Gait Kinetics, Kinematics, and Speed, and Self-Perceived Function in Patients with Knee Osteoarthritis

Exclusion criteria: those with other lower extremity injuries (orthopaedic, cardiovascular, neurologic, etc.) which are currently hindering their ability to ambulate, those with current complaints of low back pain, those who have undergone bilateral total knee arthroplasty, those with concomitant diagnosis of rheumatoid arthritis, those persons not able to ambulate independently with or without an assistive device, those who have received a corticosteroid injection within the past two months, those who have received a hyaluronic acid injection in the past six months, and those persons currently enrolled in a core training program as part of formal physical therapy or physical fitness.

3.3 Special populations will not be included in this investigation for the following reasons:

Adults unable to consent, individuals who are not yet adults, pregnant women, and prisoners will not be included in this investigation. Adults unable to consent will not be included since following directions and participating in an intervention program with active participation will be required. Minors will not be included since they do not meet the inclusion criterion for age ($>/=$ 40 years old). Pregnant women will not be included since many of the core exercises would need to be adapted in order to safely prescribe exercises tailored to that population, in addition to certain core contractions being contraindicated. Prisoners will not be included since they would not be able to attend all the intervention sessions.

4.0 Study-Wide Number of Subjects*

4.1 NA.

5.0 Study-Wide Recruitment Methods*

5.1 NA.

5.2 NA.

5.3 NA.

6.0 Multi-Site Research*

6.1 NA.

6.2 NA.

6.3 NA.

PROTOCOL TITLE: The Effects of Core Activation and Stabilization Training on Gait Kinetics, Kinematics, and Speed, and Self-Perceived Function in Patients with Knee Osteoarthritis

7.0 Study Timelines*

7.1 Each participant with KOA will actively participate in the study eight weeks, depending on the participants scheduling abilities. This will require 10-12 hours total of participation. Participants in the control group are the exception, as they will only be required to attend one session for full participation. This single session will last about 1-2 hours. It is anticipated that it will take approximately 12-18 months to enroll all study participants, with completion of data collection/analyses within this same timeline.

8.0 Study Endpoints*

8.1 The primary endpoint of this investigation will be the completion of all data collection, with all participants in both the control and experimental groups having concluded their participation.

The secondary endpoint will be the completion of all data analysis, and preparation for dissemination of the research findings.

8.2 NA.

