9.0 Procedures Involved*

9.1 This investigation will be divided into three parts, each associated with one of the specific aims detailed in Section 1. All procedures will be performed in the School of Allied Health Professions, either in the Motion Analysis Laboratory (Gait Lab) or the Rehabilitation Faculty Practice (RFP) Clinic.

Part 1: Compare age and gender matched healthy controls and KOA groups on kinetics, kinematics, and gait speed during self-selected speed via a between groups analysis across the dependent variables, and determine if those differences in the KOA group have a predictive relationship with their KOOS scores.

Part 2: Within-group comparison of both groups (with and without volitional TA activation) and between-groups (control group versus KOA group). Compare pain levels during both conditions via NPRS for the KOA group. Participants will wear biofeedback under both conditions, and all condition trials will be randomized. Alarm or verbal cue will be provided at 30% MVIC, and two electrodes placed over TA/obliquus internus (OI) just medial to anterior superior iliac spine (ASIS). A comparison of TA activation will be performed both within and between groups.

Part 3: Within-groups comparison of KOA group (pre-treatment and post-treatment; six-week training program) on kinetics, kinematics,

PROTOCOL TITLE: The Effects of Core Activation and Stabilization Training on Gait Kinetics, Kinematics, and Speed, and Self-Perceived Function in Patients with Knee Osteoarthritis

and gait speed during self-selected paced ambulation. A comparison of KOOS scores before and after treatment will be performed as well.

9.2 Once recruitment (see 22.0) and informed consent (see 27.0 and 28.0) are completed:

Part 1: All participants will undergo anthropometric data collection first, including weight, height, leg length, knee joint width, and ankle joint width. Age matching will be done within +/- 5 years between the two groups. Reflective markers will then be placed on bilateral lower extremities following the Plug in Gait Model. EMG electrodes will be placed bilaterally just medial to the ASIS, over the TA/OI. The Gait Lab will undergo calibration, and the participant will undergo a static trial. In participants with bilateral KOA, the most painful limb, identified by subjective report, will be used in the data collection procedures. Healthy controls will undergo analysis of their dominant limb by indicating with which leg they would kick a ball.

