11.0 Data Management* and Confidentiality

- 11.1 Data analysis will be performed by the PI, with the assistance of the sub-investigator. The PI will use the latest version of SPSS available to the PI on his personal laptop computer (see 11.3 for security details). The kinetic, kinematic, and speed data will be analyzed together, either by a MANOVA (if assumptions are met) or separate ANOVA/mean comparison analyses with Bonferroni corrections, while the pain NPRS and KOOS scores will be analyzed each individually via means comparisons. The EMG data will be analyzed via a 2x2 ANOVA or separate means comparisons. If the groups have significantly different mean BMIs, then it will be included in the kinetic and kinematic analysis as a covariate. The predictive relationship between the number of exercise sessions and the change observed within the KOA group for each variable will be analyzed via regression analysis.
- 11.2 An *a priori* power analysis was performed to determine the number of participants required to achieve significance for the variables of highest interest in the investigation. Data from previous publications on these variables were used in the power analysis. These include the following: T₁ between¹⁶ and within ([name], [name], unpublished data, May 2018) groups, F₂ between and within groups,¹⁸ KAM between and within groups,¹⁷ KFA between¹⁴ and within²⁶ groups, and gait speed between¹⁶ and within²⁷ groups for the kinetic and kinematic analyses. Additionally, the KOOS²⁸ was examined for within-group means comparison. The PI used G*Power (Heinrich-Heine-University Düsseldorf, Düsseldorf, Germany) for the purposes of these analyses. It was determined that 45 participants would be required, except for the KFA which would require a larger sample size. Since this variable will be collected concurrently along with the other kinetic and kinematic data, and all the other variables of interest are appropriately powered at a much lower sample size, we felt confident proceeding regardless of being underpowered for one of these five dependent kinetic/kinematic variables of interest.

Since this study involves a six-week intervention, an attrition rate of 10% was assumed, so a total of 50 participants (25 healthy controls and 25 with KOA) will be recruited. Data analysis will be completed

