PROTOCOL TITLE: The Effects of Core Activation and Stabilization Training on Gait Kinetics, Kinematics, and Speed, and Self-Perceived Function in Patients with Knee Osteoarthritis

intermittently throughout data collection, and if significance is achieved prior to 50 participants completing their participation, recruitment will be discontinued, and only those in the study will be allowed to complete the study. This will be done in an effort to reduce the number of people undergoing this less than minimal risk investigation.

- 11.3 The kinetic and kinematic data will be stored on the computer system in the Gait Lab. This lab is key accessible by the faculty of the SAHP. The computer system is password protected, with the PI and the sub-investigator being the only two individuals who currently know that password. Other faculty members would need to get the password from these two investigators for their own research activities unrelated to this investigation. The data will be backed up on an external hard drive belonging to the two investigators. No personal identifying information will be included in this data, as the participants will be identified by their participant identification numbers. The key to these identifiers will be the signed consent forms maintained by the PI that have both the participants' names and identification number on them. These forms will be maintained in the PI's office (SAHP Rm 2-234) which is key access, in a compliance binder. The data collection forms and KOOS questionnaires will also be located in this binder, with only the identification number on them. All of the deidentified raw data, including kinetic, kinematic, gait speed, NPRS ratings, and KOOS scores will also be maintained on the PI's personal laptop and work desktop computers for the purposes of data analysis, and preparations for dissemination after the completion of the data collection and analysis. Both of these computers are password protected. This de-identified data will be backed-up on the PI's personal flash drives.

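### Both endpoints in section 8.1 are project milestones, so no measured outcome is primary in any of the three parts and no test is designated to decide them.

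*Combined protocol and SAP*

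**What the plan says.** Section 8.1 has two statements. The first is "The primary endpoint of this investigation will be the completion of all data collection", once all participants in both groups have finished. The second is "The secondary endpoint will be the completion of all data analysis", with preparation for dissemination. Section 8.2 is marked not applicable.

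The measured outcomes appear in section 1 as eight hypotheses under three aims. They cover five gait variables (T1, F2, KAM, KFA and speed), KOOS, NPRS and EMG. None is marked primary.

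Three other places bear on priority:

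- **Section 2.2** reports a pilot signal on T1.
- **Section 2.3** says the investigators want to improve self-perceived function and gait speed, with kinetics and kinematics as the route.
- **Section 11.2** bases the sample size on six variables (the five gait variables and KOOS), which it treats as those of most interest. It does not order them.

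Section 11.1 analyses the gait variables together by MANOVA, or separately with Bonferroni corrections, and does not give the family size. NPRS and KOOS are each compared alone. EMG gets a 2x2 ANOVA or separate comparisons. The number of exercise sessions is related to change by regression. No correction is stated for these. Section 11.2 adds that "if significance is achieved prior to 50 participants completing their participation, recruitment will be discontinued", without naming the variable or comparison.

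**The concern.** A primary endpoint fixes in advance which result answers the study question. A milestone cannot do that: it is reached whatever the data show. With eight hypotheses on eight kinds of measurement and no designated test, the reader of the final report cannot tell a planned main result from one picked out because it was significant. The hypotheses on gait, pain and KOOS change are also non-directional, so a change either way would confirm them.

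The gap reaches the conduct of the study too. Section 11.2 lets recruitment end on significance, and with no primary outcome that trigger points to no particular test. The problem does not depend on the stopping rule, however. With recruitment fixed at 50, the final conclusion would still rest on no designated comparison.

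**Working it through.** **The plan's own figure.** Section 11.2 requires 45 participants and assumes 10% attrition: 45 / (1 - 0.10) = 50, which matches. The 45 cannot be rebuilt, because alpha, power and effect sizes are not given. The N of 50 is not affected by this point.

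**Counting the tests.** Section 11.2 refers to "one of these five dependent kinetic/kinematic variables of interest", so each gait comparison is a family of five.

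| Source | Tests |
|---|---|
| Aim 1 H1, gait in KOA "as compared to healthy controls during self-selected paced ambulation" | 5 |
| Aim 1 H2, gait differences that "will have a significant predictive relationship to their scores on the KOOS" | up to 5 |
| Aim 2 H1, gait with activation: within KOA 5, between groups 5 | 10 |
| Section 9.1, Part 2, the same within controls | 5 |
| Aim 2 H2, NPRS | 1 |
| Aim 2 H3, EMG (three effects of a 2x2 ANOVA) | 3 |
| Aim 3 H1, gait before v after | 5 |
| Aim 3 H2, KOOS before v after | 1 |
| Aim 3 H3, sessions predicting change | 5, or 6 with KOOS change |

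The total is 5 + 5 + 10 + 5 + 1 + 3 + 5 + 1 + 6 = 41, or 40 with five session regressions. Leaving out the within-control tests gives 35. Four separate EMG comparisons in place of three effects give 42.

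**Error with the stated gait correction.** Assume two-sided alpha 0.05, all null hypotheses true, independent tests, and Bonferroni within each gait family (0.05 / 5 = 0.01). Gait tests under correction: 5 + 10 + 5 + 5 = 25. Then:

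P(at least one false positive) = 1 - 0.99^(gait tests) x 0.95^(other tests)

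- 41 tests (25 gait, 16 other): 1 - 0.778 x 0.440 = 66%.
- 36 tests, dropping the five Aim 1 regressions because H2 concerns only differences found under H1 (25 and 11): 1 - 0.778 x 0.569 = 56%.
- Other readings that keep those regressions: 35 tests (20 and 15) give 62%, 40 tests (25 and 15) give 64%, and 42 tests (25 and 17) give 67%.
- MANOVA in place of each gait family leaves about 20 tests before univariate follow-up: 1 - 0.95^20 = 64%.

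**Correlation.** The 41-test case was simulated with the same thresholds and an assumed common correlation of 0.3, 0.5 or 0.7. The result was about 53%, 40% or 27%.

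**No correction at all.** 1 - 0.95^41 = 88%. This ignores section 11.1 and serves only as an upper guide.

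**After naming three primaries.** With one per part, each at 5% and independent: 1 - 0.95^3 = 14%. With Bonferroni across the three, each is tested at 0.05 / 3 = 0.0167 and the total is at most 5%.

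**The case against.** The best defence is that section 8.1 uses the word endpoint for the study's finishing point, and that the real outcomes and hypotheses are set out in section 1. The plan also has some priorities: six variables carry the sample size, NPRS and EMG are outside that list, and section 2.3 puts function and gait speed ahead of the mechanics. The gait variables are protected within each family. The study has three parts with separate aims, so pooling every test into one error rate is the reviewer's choice.

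Much of this stands. A reader might infer from section 8.1 that some 40 tests have equal standing and that the plan runs an 88% risk of a false positive. The documents do not support that. They give a partial priority list, section 11.1 corrects the gait tests, the Aim 1 regressions are conditional, and outcomes taken from the same walking trials are unlikely to be independent. A reader might also infer that the study counts as a success if anything is significant. The documents state no success criterion, so that goes beyond the text.

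The designation is still missing. The six variables account for 36 of the 40 tests (all but NPRS and the three EMG effects), so the list does not pick out a result. Sections 2.2, 2.3 and 11.2 point to different leads. Correction within a gait family limits error there, but does not say which comparison decides a part, and does not reach KOOS, NPRS, EMG or the regressions.

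**Conclusion.** The point holds. Section 8.1 states endpoints of the wrong kind, and nothing elsewhere supplies a primary outcome or comparison for Parts 1, 2 or 3. With the plan's own gait correction credited, the chance of at least one false positive across the three aims is about 56 to 66%. That rests on alpha 0.05, independence, all nulls true, and a Bonferroni family of five, none of which the documents state. Positive correlation lowers it, to about 27% at a common correlation of 0.7 for 41 tests. Inflation from the repeated analyses in section 11.2 is not included. The size therefore depends on the assumptions, but the absence of a designated test does not.

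**What to change.** Rewrite section 8.1, before any further look at the data, to name one primary outcome and one comparison for each part from the outcomes already collected. The choice is the investigators'. Options with support in the documents are:

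- **Part 1:** T1 or gait speed, KOA v control.
- **Part 2:** T1 with v without activation, in the KOA group.
- **Part 3:** change in KOOS.

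Label all other outcomes and comparisons secondary, and move the two milestones to the timeline in section 7.

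In section 11.1, state alpha and choose one of two positions: each part is a separate question tested at its own 5% and reported as such, or a Holm or Bonferroni correction applies across the three primaries. In section 11.2, tie each use of significance to the named outcomes.

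The change needs no new visits, measurements or participants. It has two costs. Significant results on other variables become secondary. A correction across parts also costs power: for a normal test with an assumed 80% power at 0.05, Bonferroni at 0.0167 gives Φ(1.960 + 0.842 - 2.394) = 66%, and an assumed 90% falls to 80%. Holm loses no more than that. Declaring the parts separate questions avoids the loss, but the 14% should then be acknowledged.
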